An initial pilot safety study will assess the risk of an infant overheating and/or experiencing lowered respiration via measurement of vital signs in a controlled clinical environment while wearing a weighted wearable blanket. Participants will also be observed for any hindrance in their ability to move due to the weighted wearable blanket. A member of the study team will be present during the intervention and continuously monitor the infant's vital signs, allowing for immediate evaluation and correction if needed. We plan to expand this study to include an at-home cohort in the near future (see secondary objective).

Objectives

- Primary Objective:**
 To pilot an investigation on the impact of weighted wearable blankets on vital signs and infant movement in healthy infants during nap polysomnogram.
- Secondary Objective:**
 To investigate the efficacy of weighted wearable blankets on sleep patterns in healthy infants during overnight sleep.

Outcome Measures/Endpoints

Endpoints	Measurement	Timeframe
Heart Rate	EKG	At start, duration of nap
Respiratory Rate	Respiratory effort belts	At start, duration of nap
Body Temperature	Manual recording (Ear thermometer)	At start (before wrapping the participant in the blanket); at the end of the study and during a (feed) break (before unwrapping the participant from the blanket)
Oxygen Saturation	Pulse oximetry	At start, duration of nap
Infant Movement	Observation	Duration of nap

Eligibility

The target population for this study are healthy infants, aged 0-12 months, weighing at least 8 or more lbs. Individuals of any sex, race or ethnicity may participate. The study population is restricted to this specific age group because the objective is focused on the safety and efficacy of weighted wearable blankets on infants.

Inclusion Criteria

- Ability of parent, caregiver or legal guardian/representative to understand a written informed consent document and choose to participate in the study.
- 0-12 months of age
- Weight \geq 8 lbs
- Gestational age \geq 37 weeks
- Health status: healthy infant without underlying cardiac, neurological, or pulmonary disorders.
- Infant is naive to a weighted wearable blanket.

Exclusion Criteria

1. Health status: medical diagnosis associated with underlying cardiac, neurological, or pulmonary disorder.
2. Weight < 8 lbs
3. Gestational age < 37 weeks
4. Gestational use of marijuana, alcohol, or illicit drugs
5. Home environment: use of cigarettes, vaping, e-cigarettes, or marijuana

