- Informed consent – we will explain the study and ask for written consent; participants will receive a signed copy of the consent to keep
 - depending on how the participant was recruited, the informed consent discussion and written consent may have already occurred virtually
- Review of inclusion/exclusion criteria
- Collection of demographic data (infant age, sex, weight) and review of clinical data (current medications, other non-pharmacologic interventions, evidence of cardiac, neurological, or pulmonary disorders) from participant medical records and parent report
- Vital signs measurements (heart rate, respiratory rate, body temperature, oxygen saturation) will be obtained at baseline and monitored throughout the sleep study
- Height and weight measurements will be obtained once, at baseline
- Participants will be placed in weighted wearable blanket such that the blanket does not cover the head/face or restrain the infant
- Participants will then be put to sleep on their backs
- Vital signs will be monitored over a 6–8-hour period with standard polysomnography equipment
- Upon infant awakening at the end of the nap, the weighted wearable blanket will be removed, and vital sign measurements will be repeated
- One week after the nap polysomnogram, subjects will be contacted by phone to complete a short questionnaire

The following stopping parameters will be used for this study. Parameters are noted when the infant is quietly sleeping and the changes observed are not due to agitation or crying. Baseline data will be recorded before and after placing the infant into the weighted, wearable blanket.

Endpoint	Stopping Parameters
Heart rate	Persistent increase by >20 from baseline for 15 minutes
Respiratory rate	Persistent increase by >10 from baseline for 15 minutes
Body temperature	Increase by more than 2° from baseline
Oxygen saturation	Persistent drop by >10% from baseline
Infant movement	Agitation and unable to settle to sleep >15 minutes

If any of the stopping parameters are met, the weighted blanket will be opened to assess if the weighted blanket is responsible for the change. If determined yes, the weighted blanket will be removed and the nap polysomnogram will be terminated.

Reportable Events

We will follow the IU HRPP Reportable Events Policy and Guidance, as needed. Severe adverse events (SAEs) will be reported to the FDA in accordance with 21 CFR 312.32.

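### A temperature taken inside the blanket is not guaranteed for every infant, because the plan gives two orders for the closing reading and names none before the blanket is opened at a stopping event

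*Combined protocol and SAP*

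**What the plan says.** **Endpoint table (Outcome Measures/Endpoints).** Temperature is listed as "Manual recording (Ear thermometer"). The first reading is "At start (before wrapping the participant in the blanket"). The later ones are "at the end of the study and during a (feed) break (before unwrapping the participant from the blanket"). Heart rate, respiratory rate and oxygen saturation are instead recorded for the whole nap.

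**Procedure list (Study Procedures).** The closing step is: "Upon infant awakening at the end of the nap, the weighted wearable blanket will be removed, and vital sign measurements will be repeated". An earlier step is: "Vital signs measurements (heart rate, respiratory rate, body temperature, oxygen saturation) will be obtained at baseline and monitored throughout the sleep study".

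**Stopping parameters (Study Procedures).** The text states: "Baseline data will be recorded before and after placing the infant into the weighted, wearable blanket". The temperature parameter is "Increase by more than 2° from baseline". When any parameter is met, "the weighted blanket will be opened to assess if the weighted blanket is responsible for the change". Removal of the blanket and termination of the recording follow only if the blanket is judged responsible.

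**Analysis (Statistical Analysis Plans, Primary Analysis).** A paired t-test compares each vital sign at baseline with its value during the intervention. The interpretation that follows describes the same test as a comparison before and after wearing the blanket. Under Sample Size Considerations, the analysis includes infants who complete both a baseline and a follow-up assessment.

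**The concern.** Overheating is one of the two risks the pilot sets out to assess. For the three continuously recorded signs, unwrapping does not erase what was captured in the blanket. For temperature it can: a spot reading taken after opening or removal is no longer an exposed value, and it cannot be recovered later.

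If the blanket does warm the infant, and some of that warmth is lost once the covering is opened, a late reading understates the change. The two descriptions of the paired test do not say which reading counts, so a post-removal value could enter it. A stopped infant could also be left out for want of a follow-up value. If stops are related to the blanket, that loss is informative, which matters more than the reduced sample size.

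**Working it through.** The plan gives no figure for this point, so there is nothing to reproduce. The check sets the passages side by side and then gives scale under stated assumptions.

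**1. Is there another source of in-blanket temperature?** The equipment list under Measures and Instruments covers EEG, EMG, EOG, ECG, effort belts, airflow, oximetry and video. It has no temperature channel. The timed temperature readings are therefore those in the endpoint table.

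**2. Which infants have a timed in-blanket reading?**

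| Course of the session | In-blanket temperature |
|---|---|
| Completed, closing reading before unwrapping | 1, plus 1 per feed break |
| Completed, no feed break, closing reading only after removal | none assured |
| Stopped on the temperature parameter | at least 1, since the trigger needs a reading |
| Stopped on another sign after a feed-break reading | at least 1 |
| Stopped on another sign, no feed break yet, blanket judged not responsible | later reading still possible |
| Stopped on another sign, no feed break yet, blanket judged responsible | none assured; the closed-blanket end reading is no longer available |

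The second and last rows are the gap.

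**3. Share of the data.** With the minimum of 10 infants, one infant is 1/10 = 10% of the temperature data.

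**4. Possible dilution.** Let δ be the true mean change, *k* the number of infants whose exposed value is replaced by a late reading, and *f* the fraction of the change lost by then. If δ is the same in every infant, the expected mean is δ(1 − *kf*/10). For *k* = 1 the loss lies between 0 and 10% of δ as *f* runs from 0 to 1. For *k* = 10, with every closing reading taken after removal and no feed-break value used, it lies between 0 and 100%. The documents give neither *k* nor *f*, so these are bounds and not an estimate.

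**5. How often might a stop occur?** The plan gives no rate. If each infant independently had chance *p* of a stopping event, the chance of at least one in 10 is 1 − (1 − *p*)^10:

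- *p* = 5%: 40%
- *p* = 10%: 65%
- *p* = 20%: 89%
- *p* = 30%: 97%

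Only some stops fall in the last row of the table, so each figure is an upper limit for that route.

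**6. Loss of precision if temperatures are missing.** Power is P(T > t(0.975, n−1)), with T noncentral t on n−1 degrees of freedom and noncentrality d√n. This assumes a two-sided 0.05 level, since sidedness is not stated. The mean change detectable with 80% power is 1.00 SD of the paired difference at n = 10, 1.07 at n = 9 and 1.16 at n = 8. For the change detectable at n = 10, power falls from 0.80 to 0.745 at n = 9 and 0.677 at n = 8.

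**The case against.** A reader might infer that some infants will have no in-blanket temperature at all, or that the two sections flatly contradict each other. The documents do not support either reading.

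- **Temperature is named among the signs monitored throughout, and baseline data are also recorded after placement.** Read literally, both give an in-blanket value. This stands as a reason not to claim that there is none. It does not close the gap. The monitoring text gives no times for temperature, and the monitoring step relies on standard polysomnography equipment, which has no temperature channel as listed. The post-placement sentence does not name temperature, and the endpoint table puts the start reading before wrapping. Even if taken, it would describe the start of exposure.
- **One reading before unwrapping and a repeat after removal would satisfy both sections.** This is correct, but neither section says so. Someone working from the procedure list alone could take only the later reading.
- **Stopping does not always end exposure.** Removal and termination are conditional on the blanket being judged responsible, and a temperature-triggered stop already implies a reading. Both points stand and narrow the gap to the cases identified above.
- **A feed break is likely.** Monitoring lasts 6–8 hours and at least 5 infants must be 0–3 months old, so many may have a feed-break reading. This also stands, but the plan does not require a feed break.
- **The bias has no size.** This stands. The documents give no cooling rate and no interval between opening and reading.

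**Conclusion.** The point holds in limited form: an in-blanket temperature is not guaranteed for every infant, and the plan does not say which reading enters the paired comparison. The direction of the bias, toward no effect, rests on two assumptions: that the blanket raises temperature, and that some of the rise is lost once it is opened or removed. The size cannot be estimated from the documents; the only firm scale is that one infant is 10% of the data at the minimum sample.

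It would go too far to say that temperature cannot inform the judgement about the blanket's role. A temperature trigger supplies a value, and a reading after opening can still be compared with baseline. The point is nevertheless more than wording, because it concerns a named safety risk and a measurement that cannot be reconstructed. It should be corrected.

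**What to change.** 1. Reconcile the endpoint table and the Study Procedures list so that the closing temperature is recorded before the blanket is opened or removed.
2. Record any post-removal temperature as a separate, labelled item, and keep it out of the value used for the intervention period in the primary analysis.
3. State in the analysis section which temperature enters the paired comparison, including for stopped infants, and align the two descriptions of the test.
4. As a data-collection item only, record a time-stamped temperature at any stopping event, marked as before or after opening. This must not change or delay the action already stated in Study Procedures.

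The cost is some reordered wording, one or two extra fields on the record form, and one more ear reading at a stopping event, with the thermometer and staff already present. The small downside is that this reading may be missing when opening is urgent; the label then shows that it is missing or was taken late.

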6. Infant is not naive to a weighted wearable blanket.

Study Design

Direct observational pilot study of the safety of weighted wearable blankets on a minimum of (10) healthy infants aged 0-12 months with nap polysomnogram. Participants will be placed in a weighted wearable blanket, in accordance with their age/weight/height, by their parent or caregiver under the supervision of a member of the study team. After being put to sleep on their back, the participant will remain in the weighted wearable blanket until completion of the nap polysomnogram.

Enrollment/Recruitment

The target number of total participants is a minimum of 10 infants. The recruitment strategy aims to achieve representation of minority groups that reflects the demographics of the population in the catchment area. At least 5 infants must be 0-3 months and all others can be any age between 0 and 12 months of age.

Participants will be recruited in a variety of ways:

Flyers will be posted in the hospital(s) and/or on campus in places frequented by potential participants (e.g., elevators, food courts, parking garage elevators) or public places such as parks, grocery stores or churches. In addition, we will provide flyers and/or brochures to the various maternity wards at Riley, University & Methodist.

Brochures will be available for patients referred to the Sleep Center at Riley or established patients at a clinic visit. Patients who are already scheduled for a sleep study, and meet eligibility criteria, will be contacted by phone and introduced to the study. If the patient is interested, we will send the brochure and the consent (either by USPS or email).

The flyers and brochures will be shared with faculty physicians (in the division of Pediatric Pulmonology, Allergy and Sleep Medicine) as well as RN and other staff in the Sleep Center and maternity wards (for informational purposes only, they will not consent subjects). We might also include the flyer in weekly newsletters and/or internal communications.

Social media ads will be placed on Facebook and/or Instagram and clicking on this ad will direct potential participants to the study's web site

(<https://dreamlandbabyco.com/pages/clinical-trial>) where they can find phone and email information for the study team.

Study Procedures

During this study, participants will have one study visit. This visit will take place in the Sleep Center at Riley Hospital for Children at IU Health.

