An adverse event (AE) is defined as any untoward medical occurrence associated with the use of a drug or device in humans, whether or not considered drug- or device-related. An SAE is defined as an adverse event or suspected adverse reaction is considered "serious" if, in the view of the investigator, it results in any of the following outcomes: Death, a life-threatening adverse event, inpatient hospitalization or prolongation of existing hospitalization, a persistent or significant incapacity or substantial disruption of the ability to conduct normal life functions, or a congenital anomaly/birth defect. Important medical events that may not result in death, be life-threatening, or require hospitalization may be considered serious when, based upon appropriate medical judgment, they may jeopardize the patient or participant and may require medical or surgical intervention to prevent one of the outcomes listed in this definition. Collection of AEs and SAEs will begin at the time of consent.

Loss of confidentiality is always a potential adverse event and will be reported per existing Indiana University and Indiana University Health policies.

Study Withdrawal/Discontinuation

Participants are free to withdraw from participation in the study at any time for any reason.

The study team may discontinue a participant from the study for any of the following reasons:

- Unacceptable adverse event(s)
- Significant study intervention non-compliance
- The participant meets an exclusion criterion (either newly developed or not previously recognized) that precludes further study participation

Statistical Considerations

Sample Size Considerations

In the pilot safety study, the total sample size will be a minimum of 10 infants. All participants will receive the same intervention. Data from all participants who complete both baseline and follow-up assessments will be included in the analysis.

Statistical Analysis Plans:

Primary Analysis (Safety)

Means and standard deviations for each vital sign will be calculated at both baseline and during the intervention. Summary statistics based on demographic and baseline characteristics will be gathered. A Paired t-test will be performed to compare the means

of each vital sign at baseline and during the intervention. We will also use a linear mixed effect model to determine differences in vital signs.

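### For heart rate, respiratory rate and oxygen saturation, the primary paired test estimates blanket effect plus sleep effect, and the stopping rules do not say which of two baselines governs

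*Combined protocol and SAP*

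**What the plan says.** The primary objective (Objectives) is "To pilot an investigation on the impact of weighted wearable blankets on vital signs and infant movement in healthy infants during nap polysomnogram".

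Study Procedures gives the order of steps: vital signs at baseline, placement in the blanket, and next "Participants will then be put to sleep on their backs". Study Design states: "After being put to sleep on their back, the participant will remain in the weighted wearable blanket until completion of the nap polysomnogram". The later unwrapped reading comes once sleep is over: "Upon infant awakening at the end of the nap, the weighted wearable blanket will be removed, and vital sign measurements will be repeated".

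On the stopping rules, Study Procedures says "Parameters are noted when the infant is quietly sleeping and the changes observed are not due to agitation or crying" and then "Baseline data will be recorded before and after placing the infant into the weighted, wearable blanket". The thresholds in the table are all changes from baseline, except the one for movement. The text does not say which of the two baselines is meant.

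On analysis (Statistical Analysis Plans), "Means and standard deviations for each vital sign will be calculated at both baseline and during the intervention", and a paired t-test compares the two means. A p-value under 0.05 is to be read as a difference in the vital sign between before and after the blanket is worn, and a larger one as no significant difference. A linear mixed model is also planned, with no term for sleep state or blanket state named. EEG staging of wake, NREM and REM is recorded (Measures and Instruments), but no analysis uses it.

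**The concern.** To learn what the blanket does during a nap, one would compare sleep in the blanket with sleep out of it. The plan schedules no sleep out of the blanket. Between the unwrapped baseline and the in-blanket recording, two things change together: the infant is wrapped and the infant falls asleep. The protocol itself treats behavioural state as important, since it reads the stopping parameters only in quiet sleep.

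Two errors are possible. A shift caused by sleep alone could be reported as a blanket effect. A sleep shift opposite to a real blanket effect could hide it, and the result would be reported as no significant difference. The second matters more in a safety pilot that is meant to precede an at-home cohort.

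The stopping rules share the gap. A quiet-sleep value is compared either with an unwrapped baseline from before sleep, or with a baseline that already contains whatever wrapping did at once.

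**Working it through.** The plan has no derived figure to reproduce: the minimum of 10 infants comes without effect size, SD or power. The check is structural, followed by illustrative arithmetic.

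**Inputs from the documents.** n = 10 (Sample Size Considerations); alpha 0.05 (Statistical Analysis Plans), sidedness not stated and taken as two-sided; thresholds of a rise >20 for heart rate, a rise >10 for respiratory rate and a drop >10% for oxygen saturation (Study Procedures).

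**Assumed, because the documents give no value.** B is the blanket effect in sleep and S the shift from pre-sleep to sleep without the blanket, both in SDs of the paired difference.

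**Step 1: which combinations are planned.**
- Unwrapped, before sleep: first baseline.
- Wrapped, before sleep: second baseline.
- Wrapped, asleep: the nap.
- Unwrapped, after awakening: reading after blanket removal.
- Unwrapped, asleep: none planned.

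**Step 2: what can be estimated.** Code each reading as (intercept, blanket, sleep).
- The primary pair is (1,0,0) and (1,1,1). That is rank 2 for 3 parameters, so only the sum of blanket and sleep effects is identified.
- Adding the wrapped pre-sleep reading (1,1,0) gives rank 3 of 3. An additive model could then separate the two, but only by assuming that the blanket acts equally before and during sleep.
- With a blanket-by-sleep term the planned readings have rank 3 of 4, and the blanket effect in sleep is not estimable. The mixed model does not change this.

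**Step 3: consequence for the test.** The paired difference has mean B + S. With df = 9, critical t = 2.262 and noncentrality √10 × (B + S), the rejection probability is P(T > 2.262) + P(T < −2.262).

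| Size of B + S | P(p<0.05) |
|---|---|
| 0 | 0.050 |
| 0.25 | 0.109 |
| 0.5 | 0.293 |
| 0.75 | 0.562 |
| 1.0 | 0.803 |

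- No blanket effect (B = 0): with S of size 0.25, 0.5 or 1.0, p<0.05 occurs in 11%, 29% or 80% of studies, against a nominal 5%.
- Real blanket effect (B = +1.0): power is 80% with S = 0, and 56%, 29% or 5% with S = −0.25, −0.5 or −1.0.

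If waking time in the blanket enters the in-blanket mean, S shrinks in proportion to the share of time asleep.

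**Step 4: consequence for the thresholds.** In raw units, let sleep lower the reading by s, let the blanket raise it by b in sleep, and let w be the immediate rise on wrapping.
- Against the before-wrapping baseline, the heart-rate rule needs b − s > 20, that is b > 20 + s. For assumed s of 5, 10 or 20, the limit is 25, 30 or 40.
- The respiratory-rate rule needs b > 10 + s. For assumed s of 2, 5 or 10, the limit is 12, 15 or 20.
- Against the after-wrapping baseline, the heart-rate limit becomes 20 + s + w, because the immediate effect w has been subtracted.
- If sleep raised the readings instead, s would be negative and the rules would fire early.

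**The case against.** The case on the other side has real weight.

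- **Baseline state is inferred.** The text never says the infant is awake at baseline, and putting an infant to sleep on the back can describe positioning. This stands as a caveat. Still, the listed order puts wrapping before sleep, and no step asks for a sleeping baseline without the blanket.
- **The pair is not firmly fixed.** The interpretation rule speaks of before and after wearing, and vital signs are repeated after removal. Before wrapping versus after removal would compare two unwrapped, non-sleeping readings and avoid this confounding, but it would not address the nap. The sentence defining the means names the intervention period, which favours the reading used here. The ambiguity is itself a reason to define the pair.
- **The magnitudes are generic.** They hold for any bias of that size in a paired test with 10 infants and are not evidence about this trial. This stands.
- **Infants are watched.** A team member monitors continuously, and when a threshold is met the blanket is opened to see whether it is responsible. That resolves a false alarm. It cannot reveal a rise that never met the threshold.

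A reader might infer three stronger things that the documents do not support.

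- **That every endpoint is confounded with sleep.** Temperature is read before wrapping and then "at the end of the study and during a (feed) break (before unwrapping the participant from the blanket", with no reading stated to be in sleep. Movement has no baseline comparison.
- **That the pilot must become a randomised crossover.** It is described as an observational pilot with one intervention for all. Splitting the recording would halve blanket time and weaken the overheating assessment, and an unweighted sack would isolate added weight instead of supplying unwrapped sleep.
- **That infants are left unprotected.** Continuous observation is planned; the main loss is in what the study can conclude.

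**Conclusion.** The concern holds for heart rate, respiratory rate and oxygen saturation. As planned, the paired test of baseline against the intervention period estimates blanket effect plus sleep effect, and the stated reading of its p-value can be falsely positive or falsely reassuring. This follows from the order of steps and needs no assumed effect size. It does rest on inferring from that order that the unwrapped baseline precedes sleep.

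How much it matters in practice is unknown, since the documents give neither the size nor the direction of the sleep effect. The figures (29% or 80% false positives at assumed shifts of 0.5 or 1.0 SD; power of 29% or 5% where 80% is expected) show sensitivity only. The unnamed threshold baseline is a separate, smaller gap. The plan should be changed, and changes to definitions and wording are enough.

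**What to change.** 1. **Define the primary pair** for these three vital signs as the unwrapped pre-sleep baseline versus the mean over blanket-on sleep epochs. Reword the interpretation rule in Statistical Analysis Plans so that the result is a change from unwrapped pre-sleep to wrapped sleep, not attributed to the blanket. State that a non-significant result is not evidence that the blanket has no effect. This makes the mixture explicit; it does not remove it.
2. **Add a state-matched contrast:** before versus after wrapping, paired within infant, both taken before sleep and in a quiet state, confirmed by EEG where recorded. State that it does not give the blanket effect during sleep.
3. **Apply each from-baseline stopping threshold against whichever of the two baselines triggers first.** For heart rate and respiratory rate this is the lower baseline, and for oxygen saturation the higher. It prevents an immediate blanket effect from being subtracted out, but it does not remove the sleep shift.

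The cost is a few sentences and IRB review of the amendment. Both baselines are already planned, so no visit, equipment or recording time is added. Item 3 will produce some extra false alarms, which the existing step of opening the blanket can resolve, at the price of disturbing some naps.

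A within-infant comparison segment of sleep is an option for the follow-on study and is not required here. Unwrapped sleep would fill the missing combination; sleep in an unweighted sack would isolate the added weight only.

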The t-statistic and corresponding p-value will be calculated at a significance level of 0.05 alpha. If the p-value is less than 0.05, this will be interpreted as a statistically significant difference in the vital sign before and after wearing the weighted wearable blanket. If the p-value is greater than 0.05, this will be interpreted as no significant difference in the vital sign before and after wearing the weighted wearable blanket.

Reporting and Documentation of Results

Measures and Instruments

Polysomnography (PSG) Equipment

PSG will be conducted using a multi-channel PSG system Respiration Alice G3 that is designed for sleep studies. The system will include the following components: Electroencephalography (EEG) to measure brain activity, Electromyography (EMG) to monitor muscle activity, Electrooculography (EOG) to record eye movements, Electrocardiography (ECG) for heart rate monitoring, Respiratory effort belts to measure chest and abdominal movements, Nasal and oral airflow sensors to monitor airflow, Pulse oximetry to measure oxygen saturation levels, and Video recording for behavioral monitoring during sleep. Prior to each PSG recording, the equipment will be calibrated according to American Academy of Sleep Medicine (AASM) guidelines to ensure accurate measurements, and quality control checks will be performed regularly to ensure proper functioning of sensors and electrodes during the study. The following physiological variables will be continuously measured and recorded during PSG:

- Electroencephalography (EEG): EEG electrodes will be placed according to the international 10-20 system to record brain activity and identify sleep stages (e.g., wake, NREM, REM).
- Electromyography (EMG): EMG electrodes will be positioned to monitor muscle activity, including chin and limb muscles, to assess muscle tone and movements during sleep.
- Electrooculography (EOG): EOG electrodes will be used to detect eye movements, which are important for distinguishing sleep stages and identifying rapid eye movement (REM) sleep.
- Electrocardiography (ECG): ECG electrodes will be placed to monitor heart rate and detect any cardiac abnormalities during sleep.
- Respiratory Parameters: Respiratory effort belts will record chest and abdominal movements to assess breathing patterns; Nasal and oral airflow sensors will measure airflow and detect apnea and hypopnea events; and Pulse oximetry will monitor oxygen saturation levels.

Privacy/Confidentiality

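### The stopping table has no written trigger for a fall in respiratory rate or for an apnea, although lowered respiration is a named risk of the study

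*Combined protocol and SAP*

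**What the plan says.** The description of the pilot just before the Objectives says the study will "assess the risk of an infant overheating and/or experiencing lowered respiration". It adds that a team member will be present and will watch the vital signs continuously, "allowing for immediate evaluation and correction if needed".

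Under Study Design the default is that "the participant will remain in the weighted wearable blanket until completion of the nap polysomnogram".

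The table under Study Procedures sets the thresholds for departing from that default. For respiratory rate it gives "Persistent increase by >10 from baseline for 15 minutes"; for heart rate, "Persistent increase by >20 from baseline for 15 minutes"; for oxygen saturation, "Persistent drop by >10% from baseline". The other two rows cover a temperature rise and an infant who is agitated and cannot settle. Meeting any row obliges the team to open the blanket and judge whether it is the cause. If it is, the blanket comes off and the recording ends.

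Measures and Instruments states: "Nasal and oral airflow sensors will measure airflow and detect apnea and hypopnea events". No stopping action is tied to those events there or anywhere else.

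**The concern.** The study names two risks, overheating and lowered respiration. Overheating has a row of its own in the stopping table. Lowered respiration does not: the only row on breathing responds to a faster rate.

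The table is the one mandatory rule in the protocol for interrupting the exposure. Followed as written, it does not act on breathing that slows or pauses unless saturation also falls far enough and for long enough. In a safety pilot in which at least 5 infants must be 0-3 months old, that leaves the decision about the named respiratory risk to whoever is at the bedside. The response may then differ between attendants and cannot be checked afterwards against a stated criterion.

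**Working it through.** The plan gives no figure to reproduce here. The check is to read each row for direction, then look elsewhere in the document for any trigger that fills the gap.

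**1. The rows of the stopping table (Study Procedures).**

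| Row | Change that triggers it | Slower breathing rate? | Apnea? |
|---|---|---|---|
| Heart rate | rise of more than 20, 15 minutes | no | no |
| Respiratory rate | rise of more than 10, 15 minutes | no | no |
| Temperature | rise of more than 2° | no | no |
| Oxygen saturation | persistent fall of more than 10% | only indirectly | only indirectly |
| Movement | agitation, not settling, over 15 minutes | no | no |

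Of the four vital-sign rows, 3 respond only to a rise and 1 to a fall. Rows triggered by a fall in respiratory rate: 0 of 5. Rows triggered by an apnea: 0 of 5. A fall in heart rate offers no second route, because that row is also upward only.

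**2. What the saturation row can catch.** Let b be baseline saturation (at most 100) and s the value during sleep. If s stays at 90 or above:

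- read as percentage points: b − s ≤ 100 − 90 = 10;
- read as a relative change: 1 − s/b ≤ 1 − 90/100 = 10%.

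Neither exceeds 10%, so the row cannot be met at 90% or above on either reading. With an assumed baseline of 95% (the documents give none), saturation would have to fall below 95 − 10 = 85% in points, or below 0.90 × 95 = 85.5% in relative terms. A slower rate or an apnea without a persistent fall of that size meets no written parameter. This shows where the row stops. It does not show that its limit is wrongly set.

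**3. Other places where a trigger might be found.**

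- Bedside monitoring (description of the pilot): allows immediate action, sets no threshold.
- Study Withdrawal/Discontinuation: the team may discontinue an infant for an adverse event it finds unacceptable. This is discretionary and has no respiratory threshold.
- Measures and Instruments: apneas and hypopneas are detected, with no action attached.
- Statistical Analysis Plans: the paired t-test and mixed model compare vital signs after the exposure. The plan gives them no stopping role.

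None supplies the missing trigger.

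**4. Which baseline a downward limit could use.** Baseline data are recorded before and after the infant goes into the blanket, and the infant is put to sleep only after that. The protocol does not say that either baseline is taken asleep, yet the parameters are read in quiet sleep. Set against an awake baseline, a downward limit might be met simply because the infant has fallen asleep. A downward limit therefore needs a quiet-sleep reference, and on this schedule that reference is taken under the weight. An apnea criterion needs no baseline.

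**The case against.** The strongest reply is that this is an attended study in a hospital sleep center. Someone watches the vital signs throughout and can act at once, the team may discontinue an infant, and nothing in Study Procedures forbids acting before a row is met. The saturation row is a downward limit on a consequence of inadequate breathing and, unlike the heart-rate and respiratory-rate rows, states no 15-minute wait. The documents contain nothing to show that an infant at 90% saturation or above must come out of the blanket. All of this stands, and it lowers the practical risk. It does not supply a written threshold. The sponsor chose to write mandatory triggers despite the attendance, so the named respiratory risk can reasonably be expected to have one.

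A second reply is that an upward limit makes clinical sense, and that lowered respiration need not mean a lower rate. That also stands. A reader might infer that the respiratory row points the wrong way; the documents do not support that, and the limit should stay.

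A third reply is that a downward limit lacks a clean reference, because no blanket-free sleep is scheduled. This is correct. It limits what such a limit can detect, and it is the reason to put most weight on the apnea criterion.

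**Conclusion.** The point holds as a gap in written coverage: 0 of 5 stopping rows respond to a fall in respiratory rate or to an apnea, in a study that names lowered respiration as a risk and records the signals needed to detect both. Confidence in that absence is high, because it rests on the text alone. Its clinical consequence cannot be sized, because the documents give no event rates. It should be fixed before enrolment.

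Two stronger conclusions might be inferred and are not supported. One is that infants are unprotected, or that staff must wait for a row to be met; the attendance, the discretionary discontinuation and the saturation row rule that out. The other is that the saturation limit is too loose, on which the documents are silent.

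The only assumptions are that the respiratory threshold of 10, printed without a unit, means breaths per minute, and the 95% baseline used for illustration. The count of rows depends on neither.

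**What to change.** Keep the upward limit and make the respiratory row two-way, for example: *sustained rise or fall of more than 10 over 15 minutes, or any apnea longer than [duration fixed by the clinical team before enrolment]*. A met criterion should lead first to opening the blanket for assessment, as the protocol already provides for the other rows.

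- **Apnea criterion.** This is the main safeguard, since it needs no baseline and uses airflow sensors and effort belts already in place. The documents give no duration, so the clinical team must set it.
- **Downward limit.** The mirrored value of 10 is only a starting point; nothing in the documents establishes symmetry, and the clinical team should confirm or replace it. State that its reference is the first period of quiet sleep. Because that period is recorded in the blanket, the limit would catch later deterioration but not a fall present from sleep onset. A blanket-free sleep reference would be an added procedure and is not requested.
- **What remains uncovered.** Shallower breathing at an unchanged rate, without an apnea, would still depend on the saturation row and the attendant.

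The cost is one amendment to the table and a few sentences, with the IRB review that Regulatory Compliance requires, and no new equipment. There would be some extra blanket openings or stopped naps, of a number the documents cannot give. An opening interrupts the exposure, and a stopped nap may drop the infant from an analysis restricted to those with both assessments. At the minimum sample each such infant is 1/10 = 10%, but 10 is a minimum, so a replacement can be enrolled.
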